## **STATEMENT OF COMPLIANCE**

The study will be conducted in accordance with the International Conference on Harmonisation guidelines for Good Clinical Practice (ICH E6), the Code of Federal Regulations on the Protection of Human Subjects (45 CFR Part 46), and the NHLBI Clinical Terms of Award. All personnel involved in the conduct of this study have completed human subjects protection training.

## REVISION RECORD

Rev No.	Date	Author	Description
1.0	20 Dec 2013	[name]	First version submitted for FDA review and starting point for filling in operational details.
2.0	12 Mar 2014	[name]	Formal approval copy for IRB which incorporates FDA feedback and fleshes out operation details for start of study.

## LIST OF ABBREVIATIONS

ADC	Apparent Diffusion Coefficient
AE	Adverse Event/Adverse Experience
CFR	Code of Federal Regulations
CRF	Case Report Form
CSOC	Clinical Study Oversight Committee
DCC	Data Coordinating Center
DCE	Dynamic Contrast Enhanced
DHHS	Department of Health and Human Services
DSMB	Data and Safety Monitoring Board
DWI	Diffusion Weighted Imaging
ESS	Endothelial Shear Stress
Fast SE	Fast Spin Echo
FFR	Federal Financial Report
FWA	Federalwide Assurance
GCP	Good Clinical Practice
HIPAA	Health Insurance Portability and Accountability Act
ICF	Informed Consent Form
ICH	International Conference on Harmonisation
IRB	Institutional Review Board
ISM	Independent Safety Monitor
MOP	Manual of Procedures
MRI	Magnetic Resonance Imaging
N	Number (typically refers to participants)
NHLBI	National Heart, Lung, and Blood Institute, NIH, DHHS
NIH	National Institutes of Health
NLDR	Non-Linear Dimensionality Reduction
OHRP	Office for Human Research Protections
OHSR	Office of Human Subjects Research
PI	Principal Investigator
QA	Quality Assurance
QC	Quality Control
SAE	Serious Adverse Event/Serious Adverse Experience

SMC	Safety Monitoring Committee
SOP	Standard Operating Procedure
SS-EPI	Single Shot Echo Planar Imaging
TOF	Time of Flight
TSE	Turbo Spin Echo
US	United States

## PROTOCOL SUMMARY

**Title:** Q-CAMP: QUANTITATIVE CARDIOVASCULAR MAGNETIC RESONANCE IMAGING AND PROFILING OF ATHEROSCLEROTIC LESIONS

**Précis:** We use MRI to evaluate the extent, as well as, the structure, composition, and functional aspects of atherosclerotic plaques in human carotid and femoral arteries in patients scheduled to undergo an endarterectomy of the aforementioned vascular beds as part of their routine clinical care. The endarterectomy specimens removed at surgery will allow a direct comparison between the MRI information obtained prior to the surgery and the histopathological analyses of the arterial specimens. The vascuCAP™ measurements of structural and functional features of the arterial wall will be performed in patients undergoing endarterectomy. Measured results will be compared in a blinded fashion with histology to assess performance of plaque profiling and build a pilot prediction model for risk scoring.

**Objectives:** Primary:

- I. Measure the bias, precision, and reproducibility of each of the functional analytes as measured by vascuCAP™ with respect to histopathologic results as ground truth, and assess their linear region and limits of quantitation.
- II. Establish performance characteristics of the structural and hemodynamic analytes, where an objective truth standard is lacking.

Secondary:

- III. Classify the target lesion according to whether the analytes suggest it is not a plaque, or if it is, which of the 8 AHA types best fits the analyte profile. Assess the accuracy of vascuCAP™'s classification against the histopathology classification.

**Population:** >=110 patients (80 carotid patients, and 30 femoral patients) scheduled for endarterectomy.

[figure not shown]
**Sites:**  
1. West Jefferson Medical Center, [name], [contact]  
2. LSU ILH, [name], [contact]

This study will be conducted within the LSU Department of Vascular Surgery at the above stated locations. Patients will be seen throughout the length of the study in both hospital and clinic settings.

**Study Duration:** 18 months for primary and secondary objectives.

**Estimated Time to Complete Enrollment:** 12 months

Schematic of Study Design:

**Final Assessments**

- I. Bias, precision, and reproducibility of each of the functional analytes as measured by vascuCAP™.
- II. Performance characteristics of the structural and hemodynamic analytes.
- III. Accuracy of vascuCAP™ classification of target lesion by AHA type.

## 2 INTRODUCTION: BACKGROUND INFORMATION AND SCIENTIFIC RATIONALE

MRI is a safe, painless, and non-invasive way to image the body interior without harmful radiation. MRI provides superior information to conventional imaging studies because it can provide additional information regarding the chemical makeup of the atherosclerotic plaque. We have recently conducted imaging studies in a specialized rabbit model of atherosclerosis [1-5] that have served as a scientific rationale for the development of a computerized image analysis toolkit, vascuCAP™ [6].

### 2.1 Background Information

The purpose of this study is to determine the magnetic resonance imaging characteristics of clinically symptomatic, atherosclerotic plaques and compare them to histopathological analyses of arterial endarterectomy specimens obtained after surgery. Atherosclerosis is a response to chronic vascular injury that results in a dysregulated, vascular inflammation fundamentally associated with abnormalities of lipid metabolism. Current commonly employed modalities utilized to image atherosclerosis, such as invasive catheterization, fail to identify plaque components and poorly predict the likelihood of the plaque to produce acute ischemic events (instability). MRI provides unparalleled soft-tissue resolution non-invasively and has the potential to characterize plaque structural and functional components without invasive procedures.

**Table 1: Analytes interrogated by vascuCAP™, understood as a multiplex assay**

Analyte	Description	Type and Units	Truth Standard
Lipid Core	Distinguished by presence of lipids, intermixed with extracellular matrix fibers, and/or necrotic tissue.	Expressed by burden in mm  and categorical variables for degree and uniformity using a 0/1/2 scale.	Histopathology considered as ground truth.
Fibrosis	Intimal presence of dense, homogeneous/organized collagen extracellular matrix with smooth muscle cells/fibroblasts embedded therein, but no appreciable lipid or necrotic tissue.	Expressed by volume in mm  and categorical variables for degree and uniformity using a 0/1/2 scale.	Histopathology considered as ground truth.
Intra-plaque hemorrhage	Presence of erythrocytes in the deeper regions of the plaque, with or without communication to the lumen or neovasculature.	Expressed by burden in mm  and confidence in %.	Histopathology considered as ground truth.
Inflammation	Accumulations of macrophages and lymphocytes in the deeper regions of the plaque that may bridge the neointima, and the media of the vessel	Expressed by burden in mm  and categorical variables for degree and uniformity using a 0/1/2 scale.	Histopathology considered as ground truth.
Vascular Leak	Composed of endothelial permeability, neovascularization, necrosis, and collagen breakdown.)	Expressed by distribution volume in mm  and categorical variables for degree and uniformity using a 0/1/2 scale.	Histopathology considered as ground truth.
Calcification	Intimal/medial presence of calcification with osteoblasts present therein, but	Expressed by burden in mm  and categorical variables for	Histopathology considered as

Analyte	Description	Type and Units	Truth Standard
	containing no appreciable lipid or necrotic tissue.	degree and uniformity using a 0/1/2 scale.	ground truth.
Remodeling Ratio	Calculated as the ratio of vessel area with plaque to reference vessel wall area without plaque	Expressed with value less than 1 for inward remodeling and greater than 1 for outward remodeling	Calculations from manual contour by radiologist as an imperfect(subjective) reference standard
% Stenosis	Calculated as the 1 - (ratio of lumen area with plaque to reference lumen area without plaque) x100	Expressed as percentage > 0 %.	Calculations from manual contour by radiologist as an imperfect(subjective) reference standard.
(maximum) Wall Thickness	Calculated by measuring the largest thickness of wall	Expressed in units of mm	Calculations from manual contour by radiologist as an imperfect(subjective) reference standard
Endothelial Shear Stress (ESS)	Tangential stress derived from the friction of flowing blood on the vascular endothelium surface and is ESS is proportional to the product of the blood viscosity and the spatial gradient of blood velocity at the wall (ESS=dv/dy).	Expressed as force/unit area (N/m  or Pascal or dyne/cm  ). Magnitude that ranges from 15 to 70 dyne/cm  over the cardiac cycle and yields a positive time average.	Literature ranges to establish plausibility (no truth standard applied in lieu of independent measurement modality).

## 2.2 Rationale

We hypothesize that *in vivo* MRI examinations of patients, when suitably acquired and analyzed with the vascuCAP™ analysis software, can provide a sufficiently accurate profile of plaque characteristics to provide an objective basis for patient management.

We propose to use MRI to evaluate the extent, as well as, the structure, composition, and functional aspects of atherosclerotic plaques in  $\geq 110$  patients (80 carotid patients and 30 femoral patients) scheduled to undergo an endarterectomy of the aforementioned vascular beds as part of their routine clinical care. These patients will be undergoing endarterectomies to mitigate their clinical risk or symptoms for things such as strokes, claudication, and critical limb ischemia. The endarterectomy specimens removed at surgery will allow a direct comparison between the MRI information obtained prior to the surgery, and the histopathological analyses of the arterial specimens. All patients will undergo a MRI examination within 30 days of the surgical procedure. Histological samples will be analyzed to identify neovascularization, intra-plaque hemorrhage, collagen types, necrotic core, and other hallmarks of plaque severity.

Histology and MRI will be co-registered, step-sectioning through the endarterectomy specimen using the suture-marked proximal and distal ends and anterior face as the anatomical markers. We create ground truth maps from histology of the excised specimens with the pre-operative MRI. This allows for careful mapping of the precise extent of plaque from the corresponding pathologic lesion onto the *in vivo* imaging. This will allow for careful training and testing of the image based classifiers to identify and characterize the plaque regions. Study duration, from

IRB approval through analysis and close of study is expected to require approximately 18 months, with 12 months targeted for subject enrollment and acquisition of samples, and 6 months to complete analyses and reporting.

## 2.3 Potential Risks and Benefits

### 2.3.1 Risks

There will be no additional risk to the patients enrolling within this study as no addition procedures or imaging will be required. Standard of care clinical workup, disease assessment, procedures, and surgical treatment will occur. Risks to patient confidentiality will be mitigated by de-identifying all patient data, specimens and samples.

Although no additional MRI outside of the standard clinical workup, the 2013 American College of Radiology (ACR) Manual on Contrast Media stated the frequency of all acute adverse events after an injection of 0.1-0.2 mmol/kg of gadolinium chelate ranges from 0.07-2.4%. The vast majority of these reactions are mild, including coldness at the injection site, nausea with or without vomiting, headache, warmth or pain at the injection site, paresthesias, dizziness, and itching. Reactions resembling an “allergic” response are very unusual and vary in frequency from 0.004% to  $\sim$ 0.7%. A rash hives, or urticaria are the most frequent of this group, and very rarely there may be bronchospasm. Severe, life-threatening anaphylactoid or nonallergic anaphylactic reactions are exceedingly rare (0.001% to 0.01%)

An important severe reaction to mention is nephrogenic systemic fibrosis (NSF). NSF is a debilitating condition whose onset is associated with gadolinium contrast injection. Primary seen in patients with GFR<30 and prior gadolinium exposure. Certain agents are known to have a higher association with NSF and are considered higher risk when administered to patients with renal impairment. Incidence ranges from 36.5/100,000 to 4/100,000.

Extravascular extravasation via infiltrated IV can occur. The incidence of extravascular extravasation in one series of 28,000 doses was 0.05%. Laboratory studies in animals have demonstrated that both gadopentetate dimeglumine and gadoteridol are much less toxic to the skin and subcutaneous tissues than are equal volumes of iodinated contrast media.

Standard risk associated with the appropriate surgical procedure will be discussed with the patient prior to operation at the time of operation consent. Minimal to no risk will be accrued by the patient via pathologic examination of the removed specimen.

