#### 4 STUDY DESIGN

A two-phase study is proposed. In the first phase, 75 surgical patients will be recruited as part of a training set; aims I-II will be evaluated with this set. In the second phase, at least a minimum of 35 and as many as 75 surgical patients will be recruited (number to be set based on the results of a statistical analysis following the first phase). Data from the second phase will be used in the definitive results to be filed in a 510(k) application to the FDA documenting the statistical performance of vascuCAP™'s ability to measure functional and structural analytes according to Aims I and II. Data collected in the second phase will also be used as additional training data for Aim III.

vascuCAP™'s performance in measuring functional analytes will be assessed using histology of specimens collected during surgery as ground truth. vascuCAP™'s performance in measuring structural analytes will be facilitated by comparing its automated segmentations against manual contours produced independently by two radiologists recruited for the study. The two radiologists will independently perform the manual contouring for all study patients, and one of these two radiologists will also perform the vascuCAP™ aided contouring after a sufficient wash-out period after the manual contouring and with appropriate blinding to their manual results.

Patients are recruited, enrolled, and analyzed with vascuCAP™. 75 patients which have been imaged and on which surgery was performed within 30 days of imaging will form the training set. An analysis will be performed and revisions to vascuCAP™ will be made, as appropriate. The sample size for the *Profiling* will be determined at this time; we denote this as  $N_{\text{profile}}$ . After analysis, the product configuration will be locked, and subsequent patient results are blinded. After  $N_{\text{profile}}$  additional patients have been imaged and on which surgery was performed within 30 days of imaging ( $N_{\text{profile}} \geq 35$ ).

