### Current Standard of Care and Deviation Thereof:

Patients will be recruited, enrolled, and the vascular bed in question analyzed with MRI and the vascuCAP™ system. For a patient to be included within the appropriate phases as described previously, any vascular operation upon the vascular bed in question must take place within 30 days of the vascuCAP™ study. MRI for carotid and femoral arterial atherosclerotic lesions is consistent with current standard of care [7]. Carotid and femoral lesion vessel distribution and percent stenosis can be accurately assessed with MRI. Thus, preoperative imagining via MRI is sufficient to construct an appropriate operative plan for individual patients. The MRI which will be required for patients to undergo will *not* be an addition to their clinical work up had they not enrolled in the study. Therefore, no additional risk will be seen by patients outside of the standard clinical workup for their specific disease.

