### 5.1 Subject Inclusion Criteria

Individuals must meet one of the following inclusion criteria in order to be eligible to participate in the study:

- a. Case subjects will be patients with documented carotid atherosclerosis, scheduled for magnetic resonance angiography and subsequent elective endarterectomy with 30 days of enrollment in the study
- b. Case subjects will be patients with peripheral arterial disease (PAD) with clinical symptoms, scheduled for magnetic resonance angiography and indicated endarterectomy of diseased areas of femoral arteries within 30 days of enrollment in the study

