### 5.2 Subject Exclusion Criteria

Individual meeting any of the following criteria will be excluded from participation in this study:

- a. Subjects with claustrophobia or inability to tolerate prior MRI studies.
- b. Subjects with metal implants that are not MRI compatible (LSU detailed checklist to be attached) including: Subjects with any type of bio-implant activated by mechanical, electronic, or magnetic means (e.g. cochlear implants, pacemakers, neurostimulators, biostimulators, electronic infusion pumps, etc.). Subjects with any type of ferromagnetic bio-implant that could potentially be displaced or damaged, such as aneurysm clips, metallic skull plates, etc.
- c. Subjects with a history of kidney disease or dialysis that are unable to receive intravenous gadolinium contrast material.
- d. Female subjects. A urine pregnancy test will be required of all female subjects of

childbearing potential prior to inclusion in this study. Pregnant or nursing females will be excluded from the study.

- e. Subjects who cannot adhere to the experimental protocol.
- f. Subjects allergic to gadolinium contrast material.

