### **5.3 Subject Withdrawal**

Subjects are free to withdraw from participation in the study at any time upon request.

An investigator may terminate a study subject's participation in the study if:

- Any clinical adverse event (AE), laboratory abnormality, or other medical condition or situation occurs such that continued participation in the study would not be in the best interest of the subject.
- The subject meets an exclusion criterion (either newly developed or not previously recognized) that precludes further study participation.

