### 6.2 Enrollment/Baseline Visit (Visit 1, Day 0)

- Review and confirm informed consent.
- Verify inclusion/exclusion criteria.
- Update any changes in demographic information, medical/dental history, medication history, alcohol and tobacco use history.
- Record results of physical and dental examinations.
- Collect blood/urine/saliva/other specimen.
- A single blood sample will be collected via antecubital venipuncture by a phlebotomist prior to MR imaging, 10-15 ml blood collected. The blood sample will be collected after verification of negative urine pregnancy test in women of childbearing potential.
- All patients will undergo a comprehensive baseline clinical assessment including evaluation of their cardiovascular risk factor profile. The specific information that will be collected is seen in the table below.

Table 2: Clinical Assessment Parameters to be Collected

Demographics	Antecedent CV Hx & Risk Factors	Clinical Parameters	Current Medications	Clinical Biochemistry	Ultrasound Findings
Age-Years Sex-% male Race Body Mass Index – kg/m  Alcohol use Tobacco Use	Smoking T2D Hypertension Hypercholesterolemia	Heart Rate Systolic BP Diastolic BP Ankle-brachial index	Aspirin Clopidogrel Statin blocker ACE/ARI Calcium channel blocker Other anti-hypertensives Oral nitrates	Total Cholesterol HDL-C, LDL-C VLDL Triglycerides Creatinine BUN AST ALT Bilirubin hsCRP Uric Acid Salivary cortisol	Thickness of anterior and distal wall of artery with lesion. Assessment of flow restriction

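### The protocol names GFR<30 as a main setting for nephrogenic systemic fibrosis, but sets no GFR cut-off for exclusion and requires no review of creatinine before the gadolinium injection

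*Combined protocol and SAP*

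**What the plan says.** Section 2.3.1 singles out NSF as a severe, debilitating reaction associated with gadolinium, "Primary seen in patients with GFR<30 and prior gadolinium exposure". It adds that some agents carry more risk in renal impairment.

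The renal exclusion, 5.2c, covers "Subjects with a history of kidney disease or dialysis that are unable to receive intravenous gadolinium contrast material". The only other exclusion tied to gadolinium, 5.2f, concerns allergy.

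At baseline, section 6.2 states: "A single blood sample will be collected via antecubital venipuncture by a phlebotomist prior to MR imaging, 10-15 ml blood collected". Table 2 lists creatinine among the biochemistry results to be collected. Section 6.3 then calls for consent confirmation, the MRI safety checklist, tattoo questions and a pregnancy test, followed by imaging with a gadolinium injection of 0.1 mmol/kg. The imaging window runs from Day 0 to Day 29.

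Section 5.3 lets the investigator end participation in two relevant situations. One is "Any clinical adverse event (AE), laboratory abnormality, or other medical condition or situation occurs such that continued participation in the study" is not in the subject's best interest. The other is that an exclusion criterion has newly developed or was not recognised before.

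**The concern.** The protocol identifies a renal level at which the harm is mainly seen and collects the analyte from which that level can be estimated, but never connects the two. Whether a patient with low GFR receives contrast depends on a known history, on someone's judgement that the patient cannot have it, or on a procedure that the text does not describe. At stake is patient safety, for a complication the protocol itself regards as serious. Bias, precision, interchangeability and classification accuracy are untouched.

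**Working it through.** The point is about absent text, so the check sets the sections side by side. The only arithmetic concerns the cost of the remedy.

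**Step 1. Threshold.** GFR<30 appears in 2.3.1 and nowhere else in the plan. Exclusion 5.2c contains no GFR or creatinine value and does not define inability to receive contrast. Prior gadolinium exposure, the other half of the setting named in 2.3.1, is not among the items collected.

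**Step 2. Pregnancy compared with renal function.**

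| | Pregnancy | Renal function |
|---|---|---|
| Exclusion | Defined by status, with a test required before inclusion (5.2d) | History plus undefined inability to receive contrast (5.2c) |
| Baseline | Negative test verified before blood is drawn (6.2) | Creatinine collected (6.2, Table 2) |
| Imaging visit | Test before each MRI; a positive result ends participation (6.3) | No step stated |

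The authors write an explicit stop when they want one. There is none for creatinine.

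**Step 3. A patient with GFR<30 and no known kidney disease.** Screening (6.1) determines eligibility from history, medications and examinations as needed, and names no renal test. At baseline (6.2) the criteria are verified and blood is taken, but the verification has no renal number to apply. Section 6.3 opens imaging to subjects who meet the criteria, with the same limitation. Withdrawal under 5.3 is permitted rather than required, and is not tied to the injection. Because the window opens on Day 0, the scan may also take place before the result is back. Followed as written, the text allows this patient to be injected.

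**Step 4. A patient with known kidney disease.** On its wording, 5.2c also needs the patient to be unable to receive gadolinium. If nobody makes that judgement, the patient remains eligible.

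**Step 5. Cost in patients.** Phase one has 75 patients; in phase two "at least a minimum of 35 and as many as 75 surgical patients will be recruited". The total is therefore 75 + 35 = 110 to 75 + 75 = 150. The documents do not give the share of patients with eGFR<30 who are not already excluded. For each 1% of patients newly excluded:

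- 110 × 0.01 = 1.1 patients to replace
- 150 × 0.01 = 1.5 patients to replace

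**The case against.** The strongest reply is that renal safety is already addressed. There is a mandatory renal exclusion, eligibility is verified at the visit where blood is drawn and again assumed at imaging, creatinine is sampled before the MRI, and 5.3 covers both an abnormal laboratory result and a criterion not recognised earlier. The 6.3 checklist and hospital contrast procedure may include a renal item. All of this stands, and it rules out one tempting inference, that the plan has no renal screening or only one route to stopping. What is missing is narrower: a number, and a time point tied to the injection.

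A second reply is that the study adds no contrast risk. Sections 2.3.1, 2.3.4 and 5 describe the MRI as part of the normal work-up, and section 5 states that "MRI for carotid and femoral arterial atherosclerotic lesions is consistent with current standard of care". A reader might still infer that the study itself creates the gadolinium exposure, since carotid inclusion asks only that patients be "scheduled for magnetic resonance angiography and subsequent elective endarterectomy" without mentioning contrast, while 6.3 fixes a dose. The documents do not support that inference: it argues from silence against explicit statements that nothing is added. Equally, routine-care status does not supply the missing check.

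A third reply is that 2.3.1 describes where NSF occurs and does not propose GFR<30 as an eligibility rule. That is fair. A fixed cut-off is a recommendation built on the protocol's own figure, not something the documents already require.

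**Conclusion.** The gap is real but modest. As written, a patient with unrecognised GFR<30 can be injected without anyone being required to look at a creatinine result that the study collects. The added risk is probably small, given that the MRI is described as routine care and that the checklist or local practice may already screen. The checklist's contents are not in the documents, so this cannot be confirmed.

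A reader might be tempted to size the harm by applying the protocol's figure, "Incidence ranges from 36.5/100,000 to 4/100,000", to 110 or 150 patients. That would not measure this gap. The figure has no stated denominator population, whereas the gap concerns only patients with low GFR who escape the history, the checklist and clinical judgement. The documents give no figure for that group, so no NSF probability is offered here. No endpoint, estimate or sample-size calculation is affected. This is a low-cost safety improvement to consider.

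**What to change.** In 5.2c, add exclusion of any patient with eGFR<30, calculated from the 6.2 creatinine or from a clinical value within a stated window. Name the estimating equation and units, since 2.3.1 gives neither.

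In 6.3, beside the pregnancy test, require documented review of that value and a question on prior gadolinium exposure before the injection. If the MRI safety checklist or the hospital contrast procedure already covers these items, cite it in 5.2c and 6.3 and state the threshold it applies.

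No new sample or visit is needed. The result must be available before the scan, so a same-day scan would need a rapid result or a recent clinical value. Recruitment cost is about 1.1 of 110 patients (1.5 of 150) for each 1% newly excluded.
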